9.4 Treatments

9.4.1 Treatments Administered

For this study the test drug is E2609 and the control drug is placebo. All study drugs are to be administered orally, QD, with food. As shown in [Figure 1](#), there will be 4 treatment arms in the MCI/Prodromal Cohort where E2609 will be administered at 3 doses (5 mg, 15 mg and 50 mg) and the comparator is placebo. In the Mild AD Cohort, there will be 3 treatment arms where E2609 will be administered at 2 doses, and the comparator is placebo. The 2 highest E2609 doses (15 mg and 50 mg) taken into Stage B, after the PK/PD and safety review from Stage A for the MCI/Prodromal group, will be used for the Mild AD population.

Study treatment will begin on Day 1 (at the study site) following Randomization and will continue for approximately 78 weeks. Please refer to [Table 7](#) and [Section 9.5.1.4.1](#) for specific information on drug administration on days when PK sampling is to be performed.

Study drug doses will remain the same for each individual subject unless the interim PK/PD analysis determines that an entire dose level requires adjustment ([Section 9.4.4](#)). See [Section 9.3.3](#) for safety-related discontinuation criteria of study drug. If a subject develops a concurrent illness during the treatment period, the investigator should discuss with the medical monitor on whether dosing with study drug needs to be temporarily suspended. As a

general clinical guideline, dosing with study drug may be resumed after resolution or stabilization of the concurrent illness, after discussion with the medical monitor.

9.4.2 Identity of Investigational Product

E2609 tablets of 5-mg, 10-mg and 25-mg dose strengths will be supplied. Placebo tablets of identical appearance will also be available. Each subject will receive 2 tablets, which combined will make up the required doses of E2609 5 mg, E2609 15 mg, E2609 50 mg, or placebo. The tablets will be supplied by the Sponsor in labeled blister packs. The product release certificates for E2609 and placebo will be included in the clinical study report for this protocol.

Subjects will be stratified and randomized, and drug will be dispensed, via an interactive voice and web response system (IxRS) system (see [Section 9.4.3](#)).

The sponsor will provide the study drugs packaged in a double-blind configuration. Each subject's study tablets will consist of either E2609 or placebo, or both (see [Section 9.4.2.3](#) for labeling details).

9.4.2.1 Chemical Name and Formula of E2609

- Test drug code: E2609
- Generic name: not applicable
- Chemical name: International Union of Pure and Applied Chemistry
- *N*-{3-[(4*aS*,5*R*,7*aS*)-2-Amino-5-methyl-4*a*,5-dihydro-4*H*furo[3,4-*d*][1,3]thiazin-7*a*(7*H*)-yl]-4-fluorophenyl}-5-(difluoromethyl)pyrazine-2-carboxamide
- Molecular formula: C₁₉H₁₈F₃N₅O₂S
- Relative molecular mass: 437.44

9.4.2.2 Comparator Drug

Not applicable.

9.4.2.3 Labeling for Study Drug

E2609 will be labeled in accordance with text that is in full regulatory compliance with each participating country and is translated into the required language(s) for each of those countries. The following information may be included but is not limited to:

- Protocol number
- For clinical study use only
- Name and address of the sponsor
- Chemical name/drug identifier (ID)
- Lot number/batch number
- Storage conditions, expiration date if necessary

9.4.2.4 Storage Conditions

Study drug will be stored in accordance with the labeled storage conditions. Temperature monitoring is required at the storage location to ensure that the study drug is maintained within an established temperature range. The investigator or designee (or if regionally required, the head of the medical institution) is responsible for ensuring that the temperature is monitored throughout the total duration of the study and that records are maintained; the temperature should be monitored continuously by using either an in-house validated data acquisition system, a mechanical recording device, such as a calibrated chart recorder, or by manual means, such that minimum and maximum thermometric values over a specific time period can be recorded and retrieved as required.

9.4.3 Method of Assigning Subjects to Treatment Groups

Subjects will be assigned to treatments based on a computer-generated randomization scheme. The randomization scheme and identification for each subject will be included in the final clinical study report for this study. The doses and number of treatment groups to be used for MCI/Prodromal subjects and for mild AD subjects are described in [Section 9.4.1](#).

Randomization will be performed centrally by an IxRS. The IxRS or clinical supply vendor will generate the randomized blister card identification numbers. At enrollment, the investigator or designee will call the IxRS to register the subject information. At randomization (Visit 3), the IxRS will assign each subject a unique randomization number.

9.4.4 Selection of Doses in the Study

It is not known how the level of CSF or brain A β reduction is related to clinical efficacy. Therefore, in this study, doses will be selected such that at steady state, they will result in 25%, 50%, and 75% reduction in CSF A β levels from baseline to cover a broad range of PD effects.

In Study 007, the relative bioavailability of a tablet formulation of E2609 in the fed and the fasted states compared with the capsule formulation in the fasted state (used in Studies 001 and 002) was investigated. It was found that when the tablet form of E2609 (50 mg) was administered with food, the exposure (ie, AUC) of the parent drug E2609 was higher, with lower maximum observed concentrations and reduced exposure to the metabolites, compared with either formulation in the fasted state.

Based on the PK/PD modeling using data from healthy volunteer Studies 001, 002, and 007, doses of 5 mg, 15 mg, and 50 mg QD administered as the tablet formulation with food in this study should achieve CSF A β reduction from baseline of approximately 25%, 50%, and 75% at steady state, respectively ([Table 3](#)).

Table 3 Predicted Steady State Plasma PK Parameters and CSF Amyloid β Reduction From Baseline

| E2609 Tablet Daily Dose (mg) With Food | E2609 Plasma $C_{max,ss}$ (ng/ml) | E2609 Plasma $C_{ss,av}$ (ng/ml) | E2609 Plasma $AUC_{(0-24h)ss}$ (ng.h/ml) | % Reduction CSF BACE1 Activity | % Reduction CSF $A\beta(1-x)$ |
|---|---|--|--|---------------------------------------|---|
| 5 | 6.2 | 3.3 | 80.3 | 16.2 | 33 |
| 15 | 18.6 | 10 | 240.9 | 36.6 | 56 |
| 50 | 62.1 | 33.5 | 803.0 | 65.7 | 79 |

$A\beta(1-x)$ = amyloid beta monomer from amino acid 1 to x, $AUC_{(0-24h)ss}$ = area under the concentration x time curve at steady state from time zero to 24 hours, BACE1 = Beta-amyloid converting enzyme, CSF = cerebrospinal fluid, $C_{ss,av}$ = average steady-state concentration, $C_{max,ss}$ = maximum plasma concentration at steady state, PK = pharmacokinetics.

The PK/PD modeling described above, which was conducted using data obtained from healthy volunteers, has also been supported by modeling of data from subjects with an underlying AD pathology (Study 101). Furthermore, external data with another BACE1 inhibitor (MK-8931) showed a similar PD effect in AD patients as in healthy volunteers (Forman, et al., 2013). Therefore we are confident that the modeling of E2609 effects in healthy subjects will be applicable for both MCI/Prodromal and Mild AD dementia patients.

The exposure of the highest dose in this study (50 mg QD tablet administered with food) is less than that of the 100 mg QD dose (capsule administered fasted) in Study 002.

The 100 mg QD dose administered for 14 days in Study 002 was well tolerated with no clinically significant changes in laboratory parameters, vital signs, or ECG parameters. On Day 15, for the 100 mg QD cohort in Study 002, there was a reduction of CD4 lymphocyte counts compared with placebo (CD4 lymphocyte counts on E2609 decreased by 3.1% from baseline, whereas the placebo control showed an increase of 8.7%), but this decrease was less than that observed at doses of 200 mg (22.9% decrease) or 400 mg (17.3% decrease). No subjects had infections or drug rash while receiving E2609 100 mg QD or at lower doses in Study 002, whereas at 200 mg and 400 mg QD, 4 subjects had symptomatic orolabial HSV1 relapses and 2 subjects at the highest dose had drug rash. The highest dose for Study 202 of 50 mg QD (tablet administered with food) is therefore expected to have a similar or better safety profile compared with the 100 mg QD capsule (administered fasted) in Study 002. Specific exclusion criteria, blinded and unblinded safety monitoring procedures, and safety criteria for discontinuation from study drug are included in this study in order to mitigate any immunology-related risk with E2609, particularly in light of the progression from 14 days of dosing (Study 002) to 18 months of dosing in this study.

Subjects in the MCI/Prodromal cohort, whether in Stage A or Stage B, will be randomized to receive either placebo or E2609 at 5 mg, 15 mg, or 50 mg QD. Subjects with mild AD (Stage B) will be randomized to receive either placebo or E2609 at 15 mg or 50 mg QD, but not the 5-mg QD dose. The rationale for not including an E2609 5-mg QD dose in the dose regimens for subjects with mild AD is that more advanced disease may require greater reduction in CSF $A\beta$ levels for comparable effects.

After 60 MCI/Prodromal subjects in Stage A have completed 4 weeks of treatment, an interim analysis of the E2609 PK and PD profiles will be used to confirm the E2609 doses to be used for Stage B, where PD is measured as reductions from baseline in CSF A β (1-x) levels. If the 95% confidence interval of the mean percentage change from baseline in CSF A β (1-x) measured after 4 weeks of treatment with a dose of E2609 does not include its intended target value (ie, 25%, 50%, and 75% reductions from baseline, respectively for E2609 at 5 mg, 15 mg, and 50 mg), PK/PD modeling will be conducted. This PK/PD modeling will use the observed PK and PD data from Stage A and will relate the average steady state plasma concentration of E2609 to steady state CSF A β (1-x) percentage reduction from baseline after 4 weeks of dosing. From this model, the new target plasma steady state concentrations of E2609 required to achieve the target levels of CSF A β (1-x) reduction will be estimated again. Dose adjustment for Stage B may be considered if it is possible to get closer to the new target plasma steady state concentrations of E2609 required to achieve the intended target levels of CSF A β (1-x) reduction than is possible with the initially planned doses, given the limitation that E2609 dose adjustments will have to be in 5-mg increments or decrements. Subjects already randomized to a dose that needs to be adjusted will be switched to the new adjusted dose and complete their treatment at this new dose.

If dose adjustment is required for Stage B, a protocol amendment reflecting the new doses will be submitted.

9.4.5 Selection and Timing of Dose for Each Subject

E2609 is administered orally, QD, with food. Study treatment will begin on Day 1 following randomization and will continue for approximately 78 weeks.

9.4.6 Blinding

E2609 and placebo will be administered as tablets of identical appearance.

During the Randomization Phase and Follow-Up Phases, subjects and all personnel involved with the conduct and interpretation of the study, including investigators, site personnel, and Eisai staff will be blinded to the treatment codes (double-blind).

Every effort should be made to keep the site staff responsible for reviewing laboratory reports and assessing AEs separate from the site staff responsible for the efficacy assessments (ie, those who are trained and certified to perform the various cognitive assessments that are undertaken in this study). Furthermore, at the site, the notes and reports relating to safety assessments must be kept separate from the notes and reports relating to efficacy.

Randomization data will be kept strictly confidential, filed securely by an appropriate group with the sponsor or CRO and accessible only to authorized persons (eg, Eisai Global Safety) until the time of unblinding, per the standard operating procedure.

The PK/PD interim analysis to confirm the E2609 doses to be used for Stage B will be conducted by an independent group. Any changes to dose will be reflected in an amendment

to the protocol and the Statistical Analysis Plan will detail how data will be handled in the primary analysis.

In the event that emergency conditions require knowledge of the study treatment given, the blind may be broken via the code breaker facility within the IxRS. Emergency procedures for revealing drug codes are given in [Section 9.5.4.5](#). If possible, before breaking the blind, the investigator should consult with the sponsor to ascertain the necessity of breaking the code.

At the conclusion of the study, all unused drug supplies are to be returned to the Eisai approved contract packaging vendor.

9.4.7 Prior and Concomitant Therapy

Medication (including over-the-counter medications) or therapy administered to the subject before the study (within 6 months of randomization) and during the study (starting at the date of informed consent) will be recorded on the Prior & Concomitant Medication eCRF or Non-Pharmacological Procedures eCRF. The investigator will record on the Adverse Event eCRF any AE for which the concomitant medication/therapy was administered. If the concomitant medication/therapy is being administered for a medical condition present at the time of entry into the study, the investigator will record the medical condition on the Medical History and Current Medical Condition eCRF.

Listings of prohibited and permitted drugs are provided in [Appendix 2](#). Prohibited medications are presented in [Listing 1](#), [Listing 2](#), [Listing 3](#), [Listing 4](#), [Listing 5](#), and [Listing 6](#). Medications that are permitted with restrictions are listed in [Listing 7](#), [Listing 8](#), and [Listing 9](#).

The following agents are not permitted before randomization (specific timeframes are shown below) and throughout the study until after the last treatment visit:

- Anticoagulants (eg, warfarin, digabatin) are not permitted for a period of 5 half-lives or 7 days (whichever is longer) before randomization
- Drugs which may cause QTc prolongation are not permitted for a period of 5 half-lives or 14 days (whichever is longer) before randomization
- Strong CYP3A4 inhibitors are not permitted for a period of 5 half-lives or 14 days (whichever is longer) before randomization
- Live vaccines are not permitted within 3 months before randomization. This does not apply to non-live/inactivated vaccines
- Ig therapy and biologic drugs are not permitted within 6 months before randomization
- Systemic or ocular immunosuppressive or immunomodulatory drugs are not permitted for a period of 5 half-lives or 60 days (whichever is longer) before randomization

Subjects taking AChEIs or memantine must meet the following criteria in order to be included in the primary analyses:

- On a stable dose for 12 weeks before the Baseline cognitive assessments at Visit 2
- Remain on a stable dose while on study

Subjects who initiate treatment with an AChEI or memantine during the study, or who change their dose of AChEI or memantine while on study, will be allowed to continue in the study, but their clinical efficacy data will be censored from the time of drug initiation for the primary analyses.

Subjects taking all other non-prohibited concomitant medications must meet the following requirements:

- Must be on stable dose for at least 4 weeks before randomization, except for medications that are administered as short courses of treatment or which are to be used intermittently as needed
- Medications that are used as needed, rather than on a stable daily basis, and which are central nervous system (CNS) active and may affect cognitive function, are not permitted during a period of 72 hours before cognitive testing

Subjects who initiate treatment with or have dose adjustment of drugs not intended for treatment of cognitive impairment during the study may continue in the study if in the opinion of the investigator this will not interfere with study procedures or subject safety, and are not prohibited above. If the subject initiates treatment for co-morbidities with a (non-prohibited) drug that may affect cognitive function, the subject should not have cognitive assessments performed until the dose has been stable for at least 4 weeks.

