As per the communication from the Food and Drug Administration (FDA) in Aug 2013, there are concerns that hypopigmentation of the skin and mucous membranes may occur with BACE1 inhibitory drugs. Although no such effects have been seen with E2609 to date, assessments by a reviewing dermatologist will be performed at regular intervals during the study. These assessments will be made centrally, using standardized photography and will specifically include evaluation of any areas of depigmentation or any rash. Dermatological assessments will be supplemented with a specific question to subjects regarding skin changes at each visit. Any such changes could be referred to the central reviewing dermatologist, and to a local dermatologist if needed, for further evaluation. See [Section 9.5.1.5.8](#) for further details.

- Baseline and on-study blood, DNA, and CSF samples will be taken and stored for all subjects. These samples may be tested in the event that a subject develops AEs that warrant further investigation (eg, if a subject develops a treatment-emergent infection) (see [Section 9.5.1.2.2](#)).
- Central reading of safety brain MRI assessments (including any MRI evidence of demyelination) will be performed at Screening, at approximately 6-month intervals during the Treatment Phase of the study, and at the final Follow-Up Visit.
- Full neurological examinations will be performed at Baseline and at regular intervals during the study by either a neurologist or a physician with comparable training and experience in undertaking neurological examinations. Details of the neurological examination are given in [Section 9.5.1.5.9](#).
- Cognitive decline will be assessed as a safety assessment (ADAS-cog₁₄, MMSE, and CBB). Of particular importance will be the assessment of reaction time testing using the detection and identification tasks on the CBB.
- An assessment of suicidality using the C-SSRS will be performed at Screening, Baseline, and at regular intervals during the Treatment Phase and Follow-Up periods of the study (see [Section 9.5.1.5.11](#)).
- All subjects, regardless of whether they complete all 18 months of treatment or discontinue study drug prematurely, will have at least 2 off-treatment Follow-Up visits (4 and 12 weeks after the last dose of study drug). More frequent safety assessments can be made as unscheduled assessments/visits during the off-treatment Follow-Up period, if clinically indicated.

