11. Any contraindications to MRI or PET scanning, including cardiac pacemaker/ defibrillator or ferromagnetic metal implants (eg, in skull; cardiac devices other than those approved as safe for use in MRI scanners). Subjects who require sedation for MRI or PET scanning as per local guidelines need not be excluded.

12. Any contraindications to lumbar puncture (LP) for CSF sampling (eg, lower spinal malformation on physical examination, local spinal infection or other abnormality, including but not limited to obesity)
13. Severe visual or hearing impairment that would prevent the subject from performing psychometric tests accurately
14. History of Ig deficiency or other immunodeficiency disorders (including subjects known to be human immunodeficiency virus positive)
15. Subjects with chronic viral hepatitis
16. A history of tuberculosis (TB). Subjects with no history of TB will be tested for previous TB exposure (eg, positive tuberculin skin test, interferon gamma release assay or other locally accepted tests) and a positive test will be exclusionary.
17. A history of ophthalmic shingles
18. A history of ocular herpes simplex virus (HSV) infection
19. Any live vaccine in the 3 months before randomization.
20. Any active infection within the last 4 weeks prior to randomization. For such cases, the timing of randomization can be extended (up to 4 weeks) to allow the infection to resolve; psychometric tests conducted at Visit 2 (eg, MMSE, CDR, etc) must be repeated.
21. Any chronic inflammatory disease that is not adequately controlled or that requires systemic or ocular immunosuppressive or immunomodulatory therapy. Subjects with:
 - a. Seasonal or perennial allergic rhinitis, asthma or chronic obstructive pulmonary disease where the condition is considered to be stable and adequately controlled by inhaled steroids need not be excluded.
 - b. Hashimoto's thyroiditis but who are stable on thyroid replacement therapy and not on systemic immunosuppressive therapy need not be excluded.
 - c. Cutaneous manifestations of immunological disease that do not require systemic immunosuppressive therapy or systemic immunomodulatory therapy need not be excluded (topical steroid treatment is permitted).
22. CD4 (T helper cells), CD8 (cytotoxic T cells), or CD19 (B cells) absolute counts below LLN and confirmed by a repeat test conducted 1 week after the initial test
23. Ig (IgG, IgA, or IgM) levels below the LLN

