9.5.1.4.2 PHARMACODYNAMIC, PHARMACOGENOMIC, AND OTHER BIOMARKER, ASSESSMENTS

Biomarkers

Subjects will be encouraged to stay at the site after completion of LP for medical observation. At Baseline, a CSF sample will be collected by LP (gravity drip method) after fasting (preferred), or at least 2 hours after the most recent meal. The timing of the Baseline LP needs to be scheduled carefully such that subsequent LPs (Visit 7 and Visit 18) can be performed between 4 and 8 hours postdose and at a similar time of day (± 1 hour) for each individual subject. At visits where cognitive tests are also performed, the LP must be performed after the cognitive tests have been completed; the subjects should rest and drink some fluid to hydrate after the cognitive tests and before the LP. The CSF sample will not be taken at the ED Visit if this visit occurs within 3 months of a previous CSF sample. The CSF sample will be used for PD assessments including but not limited to CSF A β (1-x), A β (1-42), t-tau, p-tau, and BACE. The plasma sample will be used for A β (1-x) analysis and may be used for exploratory biomarker analyses (eg, miRNA). A β (1-x) in both CSF and plasma will be measured using a commercially based enzyme-linked immunosorbent assay (ELISA). The pre- and post-screening analysis of CSF A β (1-42), t-tau, and p tau will be performed using ELISAs. BACE1 levels will be measured using internally developed fluorescence resonance energy transfer and ELISA based assay(s). Substrates of BACE1 inhibition may also be explored using Western blots or other amenable methodology if clinical observations warrant and if analytes can be reliably tested in samples collected.

The blood sample collected for PD analyses at Baseline should be collected shortly after completing the LP at Baseline. The sample should be collected at fasting or at least 2 hours after the most recent meal.

At the Baseline Visit, CSF and blood samples will be collected and stored for determination of prior exposure to any suspected infective agents in the event that the subject develops treatment-emergent AEs that warrant further investigation (eg, treatment-emergent infection). Testing may include, but not be limited to, serological tests, viral titer by quantitative polymerase chain reaction, or human leukocyte antigen genotyping.

Blood samples will be collected for PD assessments as specified in [Table 6](#) and [Table 7](#). See Section 9.5.1.4.2 for further details.

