9.5.2 Schedule of Procedures/Assessments

9.5.2.1 Schedule of Procedures/Assessments

[Table 6](#) presents the Schedule of Procedures/Assessments for the Prerandomization Phase. Screening assessments will be organized into 4 tiers (see below and [Figure 2](#)).

[Table 7](#) presents the Schedule of Procedures/Assessments for the Randomization Phase.

Table 6 Schedule of Procedures/Assessments in Study 202: Prerandomization Phase (Visit 1 and Visit 2)

| Phase | Prerandomization | |
|--|------------------|----------|
| | Screening | Baseline |
| | 1 | 2 |
| Procedures/ Assessments (to be completed in a maximum of 50 days) | | |
| Informed consent (subject and caregiver or informant) | X (Tier 1) | |
| Demographics | X (Tier 1) | |
| Medical history ^a | X (Tier 1) | |
| Prior / concomitant medications ^b | X (Tier 1) | X |
| Vital signs including weight ^c | X (Tier 1) | X |
| Height | X (Tier 1) | |
| Complete physical examination | X (Tier 1) | |
| Routine physical examination | | X |
| CBB and ISLT ^d | X (Tier 1) | X |
| MMSE ^d | X (Tier 1) | X |
| CDR ^d | X (Tier 1) | X |
| FAQ ^d | X (Tier 1) | X |
| ADAS-cog14 ^d | | X |
| 15-item Geriatric Depression Scale | X (Tier 2) | |
| Modified Hachinski ischemic scale | X (Tier 2) | |
| C-SSRS | X (Tier 2) | X |
| 12-lead ECG ^e | X (Tier 2) | X |
| Blood and urine for clinical laboratory tests ^f | X (Tier 2) | X |
| Blood for lymphocyte subset analyses ^g | X (Tier 2) | X |
| Blood for Ig analyses ^h | X (Tier 2) | X |
| Blood for viral screen ⁱ | X (Tier 2) | |
| Blood for thyroid function tests ^j | X (Tier 2) | |
| Blood for vitamin B12 test | X (Tier 2) | |
| Test for previous TB exposure | X (Tier 2) | |
| Urine drug screen | X (Tier 2) | |
| Serum pregnancy test (females of childbearing potential only) | X (Tier 2) | |
| Urine pregnancy test (females of childbearing potential only) | | X |
| Safety and Volumetric MRI ^k | X (Tier 3) | |
| Amyloid PET scan ^l | X (Tier 4) | |
| Inclusion and Exclusion criteria | X (All tiers) | X |
| Adverse events | X (All tiers) | X |
| CSF sampling for PK, PD and storage ^m | | X |
| Blood sample for PK assessments ⁿ | | X |
| Blood sample for PD and exploratory biomarker assessments ^o | | X |
| Blood sample for pharmacogenomics | | X |
| Blood sample for storage for immune status ^p | | X |
| Blood sample for PBMC isolation | | X |
| Blood sample for viral characterization ^q | | X |
| Centralized dermatological assessment via photography ^r | | X |

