| Neurological examination ^s | | X |
| Ophthalmic assessment ^t | | X |

Notes for Table 6

AChEI = acetylcholinesterase inhibitor, AD = Alzheimer's disease, ADAS-cog₁₄ = Alzheimer's Disease Assessment Scale - Cognitive subscale (14 items), CBB = CogState Brief Battery, CDR = Clinical Dementia Rating, CMV = cytomegalovirus, CSF = cerebrospinal fluid, C-SSRS = Columbia Suicide Severity Rating Scale, ECG = electrocardiogram, FAQ = Functional Assessment Questionnaire (also known as the Functional Activities Questionnaire), HBsAg = hepatitis B surface antigen, HCVAb = hepatitis C virus antibody, HSV1 = herpes simplex virus 1 (orolabial herpes), HSV2 = herpes simplex virus 2 (genital herpes), Ig = immunoglobulin, INR = International Normalized Ratio, ISLT = International Shopping List Task (immediate and delayed recall), LP = lumbar puncture, MMSE = Mini Mental State Examination, MRI = magnetic resonance imaging, PBMC = peripheral blood mononuclear cell, PD = pharmacodynamics, PK = pharmacokinetics, PET = positron emission tomography, PT = prothrombin time, PTT = partial thromboplastin time, TB = tuberculosis.

Note: Screening assessments/procedures have been organized into 4 distinct tiers. All assessments and procedures in each tier should be completed (see [Figure 2](#)), and eligibility to continue confirmed, before any assessments/procedures from the next tier commence. Similarly, all screening assessments and procedures must be completed, and eligibility to continue in the study confirmed, before any baseline assessments and procedures commence. Adverse events and eligibility against inclusion and exclusion criteria must be assessed at each stage within the Screening Visit and at the Baseline Visit.

Note: All screening and baseline assessments are to be completed within 50 days. The interval between availability of the results of the last screening assessment (PET scan) and the first baseline (Visit 2) assessments should be as short as possible and ideally should not exceed 7 days. Visit 3 (Randomization) (see [Table 7](#)) should occur 7 to 10 days after completion of the Baseline visit (Visit 2) and confirmation of eligibility to continue in the study, unless additional time is required to take Exclusion Criterion #19 into account. Thus, the total Prerandomization Phase may be up to 60 days.

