| Antipsychotic/ anti-emetic/ schizophrenia/ nausea | | |
| Chlorpromazine | Thorazine | |
| Gastrointestinal stimulant/ heartburn | | |
| Cisapride | Propulsid | |

Listing 1 Drugs with High Risk of Torsades de Pointes or QTc Prolongation

| Generic name | Brand name (Names shown are not exhaustive and are examples only; names may be the ® or ™) | Comments |
|--|--|---|
| Antinausea/ nausea | | |
| Domperidone | Motillum | Not available in the United States |
| Sedative; antinausea/ anesthesia adjunct, nausea | | |
| Droperidol | Inapsine | |
| Antibiotic; gastrointestinal stimulant/ bacterial infection; increase gastrointestinal motility | | |
| Erythromycin | Erythrocin; E.E.S. | Incidence in females greater than males |
| Antipsychotic/ schizophrenia | | |
| Haloperidol | Haldol | When given intravenously or at higher than recommended doses, risk of sudden death, QT prolongation, and torsades increases |
| Mesoridazine | Serentil | |
| Thioridazine | Mellaril | |
| Opiate agonist/ pain control, narcotic dependence | | |
| Levomethadyl | Orlaam | |
| Methadone | Methadose; Dolophine | Incidence in females greater than males |
| Anti-infective/ pneumocystis pneumonia | | |
| Pentamidine | Pentam; NebuPent | Incidence in females greater than males |
| Antipsychotic/ Tourette's tics | | |
| Pimozide | Orap | Incidence in females greater than males |
| Antilipemic/ hypercholesterolemia | | |
| Probucol | Lorelco | No longer available in United States |
| Anticancer | | |
| Arsenic trioxide | Trisenox | Used for leukemia |
| Vandetanib | Zactima | Used for thyroid cancer |

Note: This list is not exhaustive.

QTc = Corrected QT interval.

Listing 2 Prohibited Medications Within 7 Days (or 5 Half-lives, Whichever is Longer) Before Randomization and Until after the Last Treatment Visit)

| Generic Name | Brand name (Names shown are not exhaustive and are examples only; names may be the ® or ™) |
|---|--|
| Anticoagulants | |
| Adeporin | Normiflo |
| Alteplase, tPA | Activase, Cathflo Activase |
| Anisindione | Miradon |
| Antithrombin III | ATryn, Thrombate III |
| Argatroban | Argatroban |
| Bivalirudin | Angiomax |
| Dabigatran | Pradaxa |
| Dalteparin | Fragmin |
| Danaparoid | Orgaran |
| Dicumarol | Dicumarol |
| Enoxaparin | Lovenox |
| Fondaparinux | Arixtra |
| Heparin Sodium | Monoject |
| Lanoteplase | Lanoplas |
| Lepirudin | Refludan |
| Pentosan polysulfate sodium | Elmiron |
| Reteplase | Retavase, Retevase |

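### The timed anticoagulant ban counts back from randomization, so its 7-day limb guarantees no drug-free time at the Baseline lumbar puncture

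*Protocol*

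**What the plan says.** The file holds two versions of the protocol body. References here are to the one that appears to be the later; it includes PT, PTT and INR among the laboratory tests.

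- **The restriction.** Section 9.4.7: "Anticoagulants (eg, warfarin, digabatin) are not permitted for a period of 5 half-lives or 7 days (whichever is longer) before randomization". The lead-in to that list extends the ban through the study until after the last treatment visit. Listing 2 in Appendix 2 is headed "Prohibited Medications Within 7 Days (or 5 Half-lives, Whichever is Longer) Before Randomization" and runs to the same end point. It also has a row for aspirin combined with clopidogrel, limited to subjects having LP in a biomarker subgroup.
- **The first LP.** Section 9.5.1.4.2: "At Baseline, a CSF sample will be collected by LP (gravity drip method"). Later LPs are at Visits 7 and 18. Section 9.2.6 makes CSF sampling general: "Baseline and on-study blood, DNA, and CSF samples will be taken and stored for all subjects".
- **The gap.** The notes to Table 6 say that Visit 3 "should occur 7 to 10 days after completion of the Baseline visit (Visit 2) and confirmation of eligibility to continue in the study". Exclusion 20 lets randomization slip by up to 4 weeks for an infection to resolve.
- **Related safeguards.** Exclusion 12 bars "Any contraindications to lumbar puncture (LP) for CSF sampling". Exclusion 10 bars an INR above 1.7 at Screening or Baseline. Table 6 schedules "Blood and urine for clinical laboratory tests" at Screening (Tier 2) and Baseline, and note f includes PT, PTT and INR in these. Table 6 also has medication review at both visits.

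**The concern.** A pre-procedure drug restriction protects a procedure only if it is counted from that procedure. Here it is counted from randomization, while the first LP takes place before the window has opened, or at best on the day it opens. A subject taking an anticoagulant on the day of the Baseline LP can comply fully with the timed rule.

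The protocol gives no reason for the ban. If the aim is to limit bleeding during treatment, randomization is a sensible anchor, but the Baseline LP is then left without a timed rule. For aspirin plus clopidogrel the listing itself makes LP the reason, yet the listing's window misses the first LP. The same section shows that a drug rule can be tied to a Visit 2 procedure: AChEIs or memantine must be "On a stable dose for 12 weeks before the Baseline cognitive assessments at Visit 2".

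What is at stake is bleeding risk from an invasive research procedure in people not yet randomized. Efficacy estimates, power and error rates are not touched.

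**Working it through.** **Inputs**

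- Window W = the longer of 7 days and 5 half-lives, counted back from randomization (Section 9.4.7, Listing 2).
- Gap G from the Baseline LP to randomization = 7 to 10 days, taking the LP on the last day of Visit 2 (notes to Table 6). An LP earlier in Visit 2 lengthens G. With the infection extension, G can reach 10 + 28 = 38 days.
- Half-lives: none are given in the protocol.

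**Check of the timeline.** Screening and Baseline take up to 50 days, and the further gap is up to 10 days: 50 + 10 = 60 days. This reproduces the stated maximum Prerandomization Phase.

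**Guaranteed drug-free days at the Baseline LP** = max(0, W − G). The floor is zero because a guarantee cannot be negative.

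Under the 7-day limb (W = 7):

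| G (days) | max(0, 7 − G) |
|---|---|
| 7 | 0 |
| 8 | 0 |
| 9 | 0 |
| 10 | 0 |
| 38 | 0 |

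**When the half-life limb helps.** It gives guaranteed time at the LP only if 5 × half-life exceeds G:

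- G = 7 days = 168 h: half-life above 168 / 5 = 33.6 h.
- G = 10 days = 240 h: half-life above 240 / 5 = 48 h.

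Because the protocol gives no half-lives, the following values are assumed for illustration:

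| Assumed half-life (days) | W (days) | Drug-free days, G = 7 | Drug-free days, G = 10 |
|---|---|---|---|
| 0.25 to 1.4 | 7 | 0 | 0 |
| 1.7 | 8.5 | 1.5 | 0 |
| 2.0 | 10 | 3 | 0 |
| 2.5 | 12.5 | 5.5 | 2.5 |

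**With the anchor moved to the Baseline LP.** The full period, at least 7 days, is guaranteed at the puncture. On the normal schedule the 7-day restriction would start 7 + 7 = 14 to 7 + 10 = 17 days before randomization, which is 7 to 10 days earlier than now.

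**Later LPs.** Visits 7 and 18 fall inside the treatment period, when the ban is in force. The gap concerns 1 of 3 scheduled LPs.

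**The case against.** **The ban may run from consent.** The lead-in in Section 9.4.7 bars these agents throughout the study, and the section's opening sentence dates the study period, for recording medication, from informed consent. On that reading the Baseline LP is covered. But randomization always falls at least 7 days after Baseline is complete, and Screening comes earlier still, so a 7-day pre-randomization window would never bind. The longer windows for other drug classes would keep some meaning, so the reading is not impossible. The text is at best ambiguous, and a site that follows the stated timeframe complies.

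**Eligibility checks already cover it.** Exclusion 12 has an open-ended list, and a clinician who regards current anticoagulation as a contraindication must exclude the subject. Medication is reviewed at Visits 1 and 2, and coagulation tests are done at both. Exclusion 24 bars clinically significant laboratory deviations. Exclusions 3 and 30 (recent TIA or stroke, history of arrhythmia) remove some likely users. This stands as real but partial protection:

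- Exclusion 12 names no drug and sets no interval.
- Exclusion 37 refers back to the concomitant-medication rules and so carries the same anchor.
- The INR limit sits under hepatic impairment, and no numeric PT or PTT limit is given.
- The Screening panel can be up to 50 days old at the LP. Baseline samples go to a central laboratory, and nothing in the protocol requires their result before the LP.

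**The antiplatelet row is already tied to LP.** It allows the combination only in subjects who will not have LP, and on the general plan nobody is in that group. This largely stands for the row's intent. The row still sits under a heading counted from randomization and refers to a CSF subgroup that the plan does not have.

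**Stronger readings to avoid.** A reader might subtract the gap from the window and infer negative drug-free time, about −3 days or, with an infection delay, −31. Such figures have no meaning; the guarantee is simply zero. A reader might also cite the superseded Listing 2, which counted from Baseline, as proof of the intended anchor. It is weak evidence, because that version's own Section 9.4.7 counted from randomization.

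**Conclusion.** The point holds as a timing gap in a safety rule. Where the 7-day limb governs, the stated rule guarantees 0 anticoagulant-free days at the Baseline LP for every permitted interval to randomization. Agents with half-lives above 33.6 h get some guaranteed time at a 7-day gap; at a 10-day gap the threshold is 48 h. The result rests on the LP falling no later than the last day of Visit 2 and on the specific timeframes governing over the general lead-in. No half-life is assumed for the main result.

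A reader might infer that the protocol endorses LP in anticoagulated subjects, or that trial results are compromised. The documents support neither. The general safeguards let an investigator exclude such a subject, the number affected is not given and is probably small, and no efficacy analysis changes. The point justifies a low-cost safety correction.

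**What to change.** 1. In Section 9.4.7 and in the heading of Listing 2, apply the anticoagulant and aspirin-plus-clopidogrel restriction for the stated period (5 half-lives or 7 days, whichever is longer) before the Baseline LP at Visit 2, continuing until after the last treatment visit.
2. In the antiplatelet row of Listing 2, replace the reference to a biomarker subgroup with all subjects undergoing LP. No separate carve-out is needed, since that wording already leaves out anyone who will not have an LP.

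The cost is a wording change in two places, with no new visit, test or procedure. The downside is that withdrawal moves 7 to 10 days earlier, before Baseline eligibility is confirmed, so a few subjects may stop a drug and then not be randomized.
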